## 11.4 End of Study Definition

The trial will end when outcome measures from the last participant entered are known.

#### 11.5 Procedures for unblinding

We do not anticipate any need to unblind participating couple during the trial. However, if emergency unblinding is required for patient safety reasons there will be a staff member at each site and an independent statistician at the PCTU with access to the arm allocation. In the event of any unblinding the CI and trial statistician will be immediately notified. The DMEC will have access to unblinded data throughout the trial, and can recommend that the trial be terminated at any time on safety grounds.

#### 11.6 Early Termination of Study

The Sponsor, Chief Investigator, Research Ethics Committee (REC) and Regulatory Authorities independently reserve the right to discontinue the study at any time for safety or other reasons. This will be done in consultation with the Sponsor where practical. In the occurrence of premature trial termination or suspension, the above mentioned parties will be notified in writing by the terminator/suspender stating the reasons for early termination or suspension (with the exception of the sponsor responsibility for notifying the Regulatory Authorities). After such a decision, the Sponsor and the Investigator will ensure that adequate consideration is given to the protection of the subjects' interest. The investigator must review all participating subjects as soon as practical and complete all required records.

#### 11.7 Long-term follow-up

The developmental function of the infants born to couples in the HABSelect Trial is of interest but outside the scope and time-frame for the Trial as it currently stands. Should further funding become available, a new observational protocol will be developed, approval gained and potential participants traced through Fertility Clinics. Informed consent will have to be obtained.

#### 11.8 Samples

#### 11.8.1 In-clinic samples collection, processing and labeling

In the IVF centre the semen samples will be assessed for HBA score (HBS) on fresh samples (i.e. prior to freezing). Some samples will be also HBS tested after thawing in the mechanistic research laboratories to test continuity. In all cases, HBS scores will be linked to the samples' respective unique ID.

Remaining semen samples following ICSI/PICSI will be used for the mechanistic evaluations. Although not mandatory, we recommend that droplets for ICSI/PICSI are returned to the remaining sperm pellet prior to centrifugation. Clinics will indicate on the appropriate CRF the semen characteristics and HBS. Samples from patients with certain conditions (i.e. chronic viral infections) may be excluded from further mechanistic evaluations. The decision to exclude these samples will be taken by Chief Embryologist in consultation with project Laboratory Leads. Processed sperm aliquots (250 µl) will be barcoded with the labels provided by the Human Biomaterials Resource Centre, University of Birmingham, prior to freezing and storage in LN2. Each aliquot will be clearly identified with the couple's unique ID number. All samples processing will be performed according to the approved standard operating procedures.

### 11.8.2 In-clinic samples logging and storage

Samples will be stored in the designated freezer or storage cask assigned for that purpose by the participating centre and a storage log maintained. All effort will be made to ensure the samples are stored separately from any other samples kept for clinical treatment or for research purposes in the participating centres. At the end of each day samples and sample information for each participant centre will be logged by the delegated staff member in the online Database.

### **11.8.3** HBS pre and post freezing Continuity assessment.

The HBS from each of the participating centres will be regularly monitored. Scores will be harvested from the on-line database every four months and continuity tested to estimate and if necessary, reduce inter-centre variation. The information will be used to alert the data manager if any centre appears to be deviating from the expected range. If necessary, additional training may be provided to counteract the effect if it is marked. However, because the *same* sample will be sent to each mechanistic lab *and* can be tracked as such, inter-centre HBS variation should not adversely affect subsequent downstream analyses

## **11.8.4** Post-clinic sample transport to the central storage

Every participating centre will store frozen samples and transfer samples in batches by courier to the Human Biomaterials Resource Centre, University of Birmingham that will act as the central repository for all HABSelect semen samples. Shipping of the samples will be arranged on a periodic basis by the trial coordinator in collaboration with the participating centres and central storage provider. Samples will be shipped to the central storage on dry ice by the dedicated service acting on behalf of Birmingham biobank and contracted by them for that purpose. Prior to being sent, samples will be checked to validate the exact content of each shipment. Each consignment will include shipping logs, courier consignment notes and temperature audit to ensure the samples are delivered in the intact condition. On arrival the central storage facility staff will check that the physical integrity of the samples have not been compromised in the transit. Study CI, sponsor and trial coordinator will be informed if such situation arises. Laboratory staff will ensure all samples are accounted for as per shipping log. All samples received will be logged in an accountability log.

All samples received into HBRC will remain there until required. At the end of the HABSelect trial any surplus semen samples from trial participants will either be biobanked at HBRC or destroyed in accordance with the couples' instructions on their consent forms.

### 11.9 Selection of Samples for Laboratory Mechanistic Assessments

The Birmingham Mechanistic Laboratory will thaw out single aliquots and cytology will be performed on all or as many of the 3730 trial samples as possible. Cytology provides an important primary benchmark on the integrity of the semen samples

The mechanistic evaluations will be performed following PCTU stratification of the clinical HBS values (three scoring strata: <50%, 50-65%, >65%, HBS). The routine cytology will then determine if there is sufficient sample available; it is anticipated that a significant proportion of the samples will have insufficient sperm for further mechanistic evaluation. However, the stratification will generate a balanced sampling framework from each trial arm across the three HBS strata. Those samples identified by PCTU from their HBS for the mechanistic evaluation will be communicated to the HBRC central sample repository. The HBRC will then coordinate sample transfer to the four mechanistic laboratories to perform the hierarchy of mechanistic test evaluations as described in Figure 5 and Table 3.

In summary, the PCTU will select the HABSelect semen samples to be used for mechanistic analysis based on HBS and communicate this to the HBRC who will arrange shipment to the appropriate Mechanistic Laboratories. This process can be reiterated until ~900\* samples have been tested with each assay across the three, <50% 50-65%, >65%, HBS strata. It is anticipated that access to screening the full complement of 3730 trial samples in order to achieve this may be required. With dynamic PCTU and Birmingham monitoring of sample selection for analysis, it will be possible to obtain high quality information for each test in each stratum even if only a minority of samples is amenable to global examination by *all* tests. Local statistical support is confident that the information can be integrated. Shipment of samples to the mechanistic labs will follow the same operating procedures as transport of the samples from the participating centres to the central storage bank.

\* Belfast will take 450 samples for analysis but will analyse them using two distinct variations of the comet assay.

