#### 13.5 Sample size - Mechanistic evaluation

The sample size for the clinical trial (3,730) is based on detecting a 5% improvement in live birth outcome at 90% power (3,266). In contrast, the mechanistic sample size is based on an estimated minimum of 180 required for logistic regression analysis of the relationship between HBS and clinical outcomes  and can therefore be far smaller. While this number accommodates the potentially limiting availability of samples with low (<50%) HB scores (estimated at ~10% or ~370), it is a minimum estimate that does not satisfy the need to more accurately specify the relationships between the mechanistic and clinical outputs of this study that are less dependent on HB scoring (such as sperm concentration). Furthermore, as indicated elsewhere, many of the samples will not be amenable to mechanistic tests. Hence, the chosen mechanistic sample size is a balance between minimum sample size requirements (180) required to link clinical and mechanistic outcomes, the need to access more samples in order to accommodate limitations in their use and the relative cost of analysis. Assuming that  $\sim$ 20% of samples can be examined by one or more tests based on cytology, only 36/180 will satisfy the criteria. Hence ~900 samples (180/36\*180) are required overall. All mechanistic tests are needed to facilitate the identification of the form of damage that compromises sperm function in relation to clinical outcome (Fig 6).

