All samples will be transferred to the Human Biomaterials Resource Centre, University of Birmingham as outlined in Section 11.9 for initial cytology. Cytology will be performed retrospectively on as many of the 3730 trial samples as required for mechanistic analysis. It will provide an important first step characterisation on the integrity of the semen samples. The rationale for banking semen samples on all trial participants is based on maximising the success of the exploratory mechanistic components of the study. The sampling has been described in Section 11.9.1. In summary, the mechanistic evaluations will be performed retrospectively following PCTU stratification by sample characteristics based primarily on the HBS to assay across the three, <50%, 50-65%, >65% HBA scoring strata, with the cytology secondarily determining if there is sufficient sample available. It is anticipated that a significant proportion of semen samples will be identified as having insufficient sperm for further mechanistic evaluation. The retrospective stratification will generate a balanced sampling

frame from each trial arm to obtain high quality information for each test in each stratum even if only a fraction of the samples is amenable to global examination by *all* tests (refer to Figure 5; Table 3).

Of note the mechanistic tests do not inconvenience participants, or their management or treatment as they use residual semen samples from the ISCI/PICSI IVF procedure.

**Figure 6**. Schematic representation of structural equation modelling showing relationship between measured quantities (boxes) and latent variables (ellipses). *DNA frag* and *Chrom* are treated as covariates in the regression model for HBS score.

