## 13.7 Mechanistic Evaluation

The mechanistic evaluation will be conducted through a structural equation modelling approach that is particularly well suited to estimating causal relationships using a combination of quantitative data and qualitative causal assumptions . DNA fragmentation will be measured though the comet assay and through slide-based acridine orange assay and summarised through the latent variable DNAfrag (Fig 6). Similarly, chromatin compaction measured by aniline blue and CMA3 assays will be summarised through the latent variable Chrom. HALO provides a separate covariate of sperm nuclear integrity. These two latent variables (DNAfrag, Chrom), and HALO are covariates in a regression model for Hyaluronan Binding Score (HBS) which in turn is a covariate for the logistic regressions for each of the clinical outcomes

(biochemical pregnancy at two weeks, clinical pregnancy at 6–8 weeks, miscarriage rate, and live birth at  $\geq$ 37 weeks. The structural equation modelling can be undertaken with the software MPLUS version 6.12.

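### Mechanistic samples are selected on HBS, HBS is then the response in the first equation of the structural equation model, and section 13.7 makes no provision for that sampling

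*Protocol*

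**What the plan says.** **Selection.** Protocol section 11.9 states that "the PCTU will select the HABSelect semen samples to be used for mechanistic analysis based on HBS", using "three scoring strata: <50%, 50-65%, >65%, HBS", and that "the stratification will generate a balanced sampling framework from each trial arm across the three HBS strata". Section 13.5 repeats the rule ("The retrospective stratification will generate a balanced sampling"), again by arm. Neither section gives a number per stratum.

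**Stratum sizes.** Section 13.5 acknowledges the "potentially limiting availability of samples with low (<50%) HB scores (estimated at ~10% or ~370" of the 3,730 planned.

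**Model.** In section 13.7 the two latent variables (DNA fragmentation and chromatin compaction) and the HALO result "are covariates in a regression model for Hyaluronan Binding Score (HBS) which in turn is a covariate for the logistic regressions". Those regressions have the pregnancy and birth outcomes as responses. HBS is therefore the response in the first equation and a predictor in the second. The section names the latent variables, their indicators, the paths and the software. It does not mention sampling fractions, weights or a likelihood adapted to the sampling.

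**Nearby text that does not settle it.** Section 11.9 expresses confidence that information can be combined when few samples receive every test, but names no method. Section 13.3 deals with missing baseline covariates and missing clinical outcomes, not with deliberate selection on HBS.

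**The concern.** Sampling on a predictor leaves a correctly specified regression slope intact. Sampling on the response generally does not: it changes the slope, the residual variance, and the means and variances of the covariates and latent variables, unless the analysis uses the sampling fractions. Here the selection variable is the response of the first equation.

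The relation of HBS to chromatin integrity is part of the primary mechanistic objective (section 6.1.1.2). An indirect effect running from damage through HBS to a clinical outcome is built on the first-stage coefficient, so it inherits any distortion there. Assaying more samples under the same allocation narrows the intervals but does not remove the distortion. Its direction depends on the HBS distribution, so it cannot be corrected by judgement afterwards.

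**Working it through.** **Inputs**

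- HBS below 50%: about 10% (370/3,730 = 9.9%), section 13.5.
- HBS at or below 65%: 121/(121 + 357) = 25%, from the US trial in Table 2 (section 5.3.2). This implies 25% - 10% = 15% in the 50-65% stratum and 75% above. This is an assumption for the present cohort; the middle stratum was varied from 10% to 20%.
- About 900 samples and about 20% usable: section 13.5.
- Damage-to-HBS correlation of 0.1 to 0.5 in size, and the shape of the HBS distribution: assumptions, since the protocol gives neither.

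**1. The plan's own figure.** 180/(36/180) = 900. It reproduces exactly.

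**2. Unequal selection if *balanced* means equal numbers.** The sampling fraction is proportional to (1/3)/stratum share: 3.33 for below 50%, 2.22 for 50-65% and 0.44 for above 65%. A low-HBS sample is then 3.33/0.44 = 7.5 times as likely to be drawn as a high-HBS one.

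**3. Effect on the slope, HBS bounded at 0-100%.** HBS was simulated as a beta variable matched to 10% below 50 and 25% below 65, with damage standardised. Slope = Cov(damage, HBS)/Var(damage), in HBS points per SD of damage. Weights are the inverse of the stratum sampling fraction.

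| Correlation | Cohort slope | Equal thirds, unweighted | Ratio | Weighted |
|---|---|---|---|---|
| -0.1 | -1.71 | -2.02 | 1.18 | -1.68 |
| -0.2 | -3.42 | -4.02 | 1.17 | -3.39 |
| -0.3 | -5.15 | -6.06 | 1.18 | -5.15 |
| -0.5 | -8.61 | -10.06 | 1.17 | -8.62 |

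**4. Other HBS shapes, equal thirds.** Normal HBS gives ratios of 1.01 to 1.09; skewed residuals give 0.88 to 0.89. Weighting recovered the cohort slope in each case.

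**5. What the allocation can be.** The two sections support different readings of 900.

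- *About 900 drawn, of which about 20% are usable (section 13.5).* Equal thirds draw 300 per stratum, or 300/370 = 81% of all low-HBS samples, and yield 300 x 0.20 = 60 usable per stratum (180 in all). This is feasible. With bounded HBS the unweighted slope is overstated by about 17-20%. Across repeated runs, nominal 95% intervals cover 91-92%, 88-91% and 76-79% at correlations of 0.2, 0.3 and 0.5. With normal HBS the overstatement is about 2-6%.
- *About 900 tested with each assay (section 11.9).* At 20% usable, 3,730 samples give 746 usable in all and 370 x 0.20 = 74 with low HBS, so 300 per stratum cannot be reached. If every usable sample is assayed, there is no selection on HBS left, provided usability is unrelated to HBS. An illustrative 74/300/526 split gives ratios of 0.93 to 0.98.

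If 300 per stratum could be assayed, bounded HBS would give coverage of 83%, 69% and 28% at the same three correlations.

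**6. Where there is no distortion.** A true slope of zero stays at zero, including a null covariate fitted beside a non-null one. The logistic slope of outcome on HBS is 0.294 in the full cohort and 0.294 in the selected sample, as expected when selection is on the predictor.

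**The case against.** The strongest case is that the document is silent rather than wrong. Section 13.7 is one paragraph, and estimator and weights for a structural equation model normally belong in a statistical analysis plan, which is not shown here. A reader might infer that the model will be fitted unweighted to equal numbers per stratum, so that its coefficients are biased by about a fifth. The protocol supports none of these steps. It never says unweighted. *Balanced* has no number attached and could mean balance between arms within strata. The section 11.9 reading of 900 rules out equal thirds on the protocol's own usable fraction. The size and even the sign of the distortion depend on an HBS distribution that has to be assumed.

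Other points also stand. The mechanistic work is described as exploratory. Comparing damage between high- and low-HBS sperm, which is part of the primary mechanistic objective, conditions on HBS and was unchanged by the selection in simulation (ratios 0.99 to 1.01). Weighting is not the only remedy: section 10.1 obtains HBS on all samples, so a likelihood fitted to all couples is an alternative, although it gave ratios of 0.91 to 0.96 under equal thirds and 0.98 to 1.00 under feasible splits. One weight per sample also fits poorly with Table 3 (section 11.9.1), where each assay has its own subset set by sperm quantity.

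These points limit the claim but do not remove it. The protocol itself fixes both the selection rule and the regression whose response is the selection variable, and it is their combination that needs handling. The counts needed to correct for it must be kept while sampling is under way, because selection is iterative and filtered by cytology.

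**Conclusion.** The point holds in a conditional form. The protocol fixes response-dependent sampling for the first equation of the model and does not provide for it. If the assayed set departs from cohort proportions and the fit ignores this, non-zero damage-to-HBS coefficients and the indirect effects that use them will be distorted.

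Under equal sampling of assumed 10/15/75% strata the size is about -12% to +20%: roughly +17 to +20% for bounded HBS, +1 to +9% for normal HBS, and -11 to -12% with skewed residuals. The 7.5-fold sampling ratio and the upper figures describe that scenario; they are not results for this trial. The distortion is nil under a null slope, nil if all usable samples are assayed (with usability unrelated to HBS), and absent from the HBS-to-outcome path. The primary clinical comparison is not involved. It should be corrected, with medium confidence in its practical size.

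**What to change.** Keep the balanced draw; over-sampling scarce low-HBS samples is sensible.

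- In section 11.9, state the intended number per arm and HBS stratum. Have the trials unit record the available, selected, usable and assayed counts by arm and stratum, and by assay because of Table 3.
- In section 13.7, state that the model accounts for the HBS-dependent sampling, either by inverse-sampling-fraction weights with robust standard errors or by a likelihood that conditions on the sampling. Report the unweighted fit as a sensitivity analysis.

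The cost is a sentence or two and a weight variable derived from counts the trials unit can hold, since HBS is scored on every sample. Intervals will be wider in some scenarios. At 60 per stratum, weighting lowered the root mean square error with bounded HBS but raised it with normal HBS, which is a reason to show both fits.

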#### 11.9.1 Mechanistic assessments

Four basic science laboratories will perform mechanistic evaluation of the collected semen samples according to the following order:

- Birmingham cytology, TUNEL, Acridine Orange (AO) stain
- Belfast -Comet

\*

- Sheffield HALO, Aniline Blue
- Leeds -TUNEL, HALO, Aniline Blue, CMA3
- semen sampling >> DDG centrifugation 40:80 **PVP-ICSI** PICSI frozen storage 2.Cytology < remaining pellet (interface) (Birm) frozen storage 🚽 (pellet) 1.HBA scoring (HBS) 3a.Comet 3b.TNL **4**.AO 5.HALO 6a.CMA3 6b.AB <50% 50-65% >65% (Belfast) (Birm/Lds) (Birm) Lds/Sheff (Lds) Lds/Sheff Sample selection < Online database

**Figure 5**. Schematic of mechanistic protocol. There is a hierarchical priority of testing, with the number carried out depending on the number (Table 2, **N**) of available sample aliquots after HBA scoring. The testing priority is 1, 2, 3a AND/OR 3b, 4, 5, 6a AND/OR 6b. If four aliquots are available, all tests can be carried out across the four centres. If three aliquots are available, going to three centres, it will not be possible to replicate tests 5 and 6 in both Lds and Sheff. If two aliquots are available, going to two centres the same restrictions will apply and additionally, only one of tests 4, 5 or 6 will be possible. All samples will be stored centrally in Birmingham HBRC; hence they can begin to process and assess samples for distribution as soon as they are ready. If following cytology (1), there is only sufficient sample for analysis at one centre, it will be Birm who carries out any additional tests. PCTU will assist in maximising the use of available samples by all mechanistic labs. Collection of sperm from the 40:80 interface will occasionally be undertaken on CI request for the mechanistic studies.

**Table 3.** Mechanistic assays are subject to a hierarchical order of importance as follows: 1.  $HBS^{CL} > 2$ .  $Cytology^{BI} > 3$ .  $(aComet^{BL} = bTunel^{BI}) > 4$ . AO stainBI > 5.  $HALO^{SH, LE} > 6$ . (aAniline BlueSH, LE = bCMA3SH, LE). It is assumed that the HBS (1) will be carried out on all samples by the clinics prior to aliquoting.

Equivalent available	Test
aliquots (N)‡	
4	2, 3a, 3b, 4, 5, 6a, 6b
3	2, 3a, 3b, 4, 5*, 6*
2	2, 3a, 3b, 4 OR 5* OR 6*
1	2, 3b, 4

CL, clinical labs; BI, Birmingham; BL, Belfast; LE, Leeds; SH, Sheffield.

\* Sent to either of the two centres carrying out these assays. To balance the numbers, tests

may be alternately carried out (OR) and in alternate centres.

‡All semen samples will be aliquoted in the IVF clinic into four equal volume samples. The cytology examine will determine the sufficiency of the sperm in each aliquot and adjustment will be made of the number of equivalent aliquots available for the mechanistic evaluation, e.g. where there is a low sperm count in the semen sample the 4 combined aliquots may only provide 1 equivalent aliquot and therefore only a limited range of mechanistic testing is available and priority will be given following a rank order of priority. In addition, Leeds and Sheffield will establish manual processes for quantifying the results of their tests and a proportion of the manually processed slides will be sent to Birmingham for automated quantitative analysis. This will satisfy continuity requirements for all other assays.

